Lovett et al reported on 339 patients who were consecutively treated for histologically confirmed basal cell (71%) and squamous cell (29%) carcinoma. A retrospective study was performed to assess local recurrence. The majority of the basal cell lesions (93%) and 97% of the SCCs were on the head. Radiation therapy was the initial treatment modality in 212 patients, and 127 patients were treated with radiation therapy after the initial surgical excision failed. Tumor control was analyzed by the type of external beam radiation therapy administered. The local control for superficial x-ray ranged from 91 to 100% reported categorically by tumor size. Electron beam ranged from 70 to 75% local control. Patients were stratified into groups by the

type of radiation beam used on the treatment. Excellent to good cosmesis was seen in 97% of the patients treated with superficial X-rays and in 78% of the patients treated with electrons, 78% of the patients treated with mixed beams, and in 80% of the patients treated with megavoltage photons. The overall complication rate (complications were defined as grade 4 toxicities) for the 310 patients whose data was available was 5.5%. Of the 217 previously untreated patients, the complication rate was 3.2%.

Silva et al report on a retrospective review of radiation therapy treatment for basal cell, squamous cell, and basal-SCC from 313 patients with 334 lesions treated. The objective of this study was to assess local control and late toxicities in patients treated with radiation therapy for the treatment of cancer of the pinna of the ear. For 270 patients, radiation therapy was the primary treatment, 50 patients received radiation therapy for recurrent cancer that had not previously undergone resection, and 12 patients received radiation therapy as an adjuvant treatment.

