#### 7.5 Secondary Endpoints

- i. Comparison of long-term toxicities related to eBx vs. Mohs treatment;
- ii. Comparison of long-term cosmetic outcomes for lesions treated for NMSC with eBx vs. Mohs;
- iii. Chronic toxicities;
- iv. Patient Survey for reporting Patient Reported Outcomes (PRO)

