#### 8 METHODOLOGY

#### 8.1 Identifying the Population

The first phase of this study will be to identify patients who completed treatment with eBx or Mohs treatment approximately 3 years ago or more prior to study onset and collect history and demographic data, and eligibility and treatment planning and treatment data retrospectively from the patient records and on source worksheets to complete a matched pair cohort study comparison.

This phase will include a review of the site's patient medical records to determine if the source documentation contains the variables that are needed to determine eligibility and which will be used in the endpoint analyses. These variables include:

- Patient Age (within  $\leq 15$  year brackets)
- Pathology report for evidence of:
  - Lesion size (cm)
  - Lesion diagnosis (BCC, SCC)
- Last treatment date for each location
- Lesion location (e.g. face, extremities, neck, nose, scalp, torso)
- Toxicities at time of prospective follow-up visit

Matching will be performed according to:

- Calendar year of treatment for equivalent follow-up
- Patient age bracket [15-year brackets or less]
- Lesion diagnosis (BCC, SCC)
- Lesion size range (< 1 cm,  $\geq$ 1 and <2 cm,  $\geq$ 2 and <3 cm,  $\geq$ 3 and  $\leq$ 4 cm)
- Location according to the methodology below:
  - o Scalp
  - Face (includes neck)
  - o Nose
  - o Ear
  - o Torso
  - Upper extremities (Arms, hands, fingers)
  - Legs (Thighs, lower leg, feet, toes)

Data Collected Prospectively:

- Cosmesis rating by physician
- Cosmesis rating by the patient
- Recurrence of cancer
- Chronic toxicities
- Patient reported outcomes (PRO) survey

Patients who return for long-term follow-up will be required to provide informed consent for both the retrospective data and the prospective data that are collected at the time of the visit.

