#### Table 1. Case Report Forms

#### **12.2 Statistical Analyses**

This is a multi-center, retrospective-prospective study comparing non-melanoma skin cancer treatment (basal cell carcinoma and squamous cell carcinoma) using Xoft electronic brachytherapy (eBx) results compared to a Mohs micrographic surgery. The lesion data will be matched on 4 categories as outlined in Section 8 and the results will be compared between the two treatment groups.

A sample size calculation comparing treatment of NMSC with eBx to treatment with Mohs micrographic surgery was done using a 1.5% historical 3-year recurrence rate for NMSC treated with Mohs, and a 2.5% non-inferiority margin. A total of 293 lesions for each treatment group will provide 80% power with a 0.05 alpha level of significance. Data from up to three hundred-twenty (320) subjects with each type of treatment will be collected to ensure a sufficient number of lesions to adequately power the study. There may be more than one lesion per patient that is matched to another lesion in the other treatment group. The total lesions will be compared in this study and the lesion count determines the number of patients that are ultimately enrolled.

The primary endpoint of freedom from recurrence and the secondary endpoints will be summarized for each treatment group and Chi-square tests performed as applicable. All tests will be 2-sided, with significance level set at 0.05, and performed using SAS (version 9.4 SAS Institute, Inc., Cary, NC).

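### Section 12.2 names only Chi-square tests for the secondary endpoints, so cosmesis ratings, if they have more than two ordered levels, may be compared by a test that ignores their order; the power lost depends on a scale the documents do not give.

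*Combined protocol and SAP*

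**What the plan says.** Section 12.2 (Statistical Analyses) gives one sentence on method for everything beyond the sample size: the primary endpoint and "the secondary endpoints will be summarized for each treatment group and Chi-square tests performed as applicable". It adds: "All tests will be 2-sided, with significance level set at 0.05". No rank, trend, ordinal-model or paired method is named anywhere.

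Section 7.5 lists as secondary endpoints "Comparison of long-term cosmetic outcomes for lesions treated for NMSC with eBx vs. Mohs" and "Comparison of long-term toxicities related to eBx vs. Mohs treatment". Section 8.1 lists among the prospective data "Cosmesis rating by physician", followed by a separate rating by the patient. Section 4 describes cosmesis in ordered words when it summarises a radiotherapy series: "Excellent to good cosmesis was seen in 97% of the patients".

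The cosmesis scale, the number of levels, any cut-point and the form in which toxicity is analysed are not stated. Sections 15.2 and 15.3 place the case report form and the patient survey in separate documents.

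**The concern.** A rating that runs from better to worse carries information in its order. A Pearson Chi-square test of two groups on k levels does not use it: the result is the same if the levels are shuffled, and the evidence is spread over k − 1 degrees of freedom. A test aimed at a shift along the scale uses one degree of freedom. If one treatment gives generally better ratings, the order-blind test is the more likely to miss it.

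Cosmesis is an objective (Section 7.3), a secondary endpoint (Section 7.5) and part of the purpose (Section 6). Section 4 also says that cosmesis after Mohs surgery may suffer, which is an expectation in one direction. A missed shift would therefore bear on a question the study sets out to answer.

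**Working it through.** **Inputs from the documents.** 293 lesions per group and two-sided 0.05 (Section 12.2). Everything else below (number of levels, category shares, odds ratio) is assumed.

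**1. The plan's own figure.** Section 12.2 uses a "1.5% historical 3-year recurrence rate for NMSC treated with Mohs, and a 2.5% non-inferiority margin" and states: "A total of 293 lesions for each treatment group will provide 80% power with a 0.05 alpha level of significance". With unpooled variance,

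n = (z₁₋α + z₀.₈₀)² × 2p(1 − p) / margin², with p = 0.015 and margin = 0.025.

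At one-sided alpha 0.05: 6.183 × 0.02955 / 0.000625 = 292.3, so 293. The figure reproduces, with power 80.1% at 293. It concerns recurrence only; no power is stated for any secondary endpoint.

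**2. Cost of the extra degrees of freedom.** Power = P(noncentral χ² with df and noncentrality λ exceeds the 95% point of central χ² with df). Choose λ so that a 1-df ordinal test has 80% power (λ = 7.85), then give the same λ to a test with k − 1 df:

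| Levels | Pearson power | Loss (points) |
|---|---|---|
| 2 | 80.0% | 0 |
| 3 | 70.9% | 9.1 |
| 4 | 64.5% | 15.5 |
| 5 | 59.5% | 20.5 |
| 6 | 55.5% | 24.5 |

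The largest loss found this way was 25.5 points (six levels, ordinal test at 70% power).

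**3. Simulation.** 293 unpaired lesions per group, 40,000 replicates, proportional-odds shift, Pearson against the tie-corrected Wilcoxon test. Each cell gives Pearson power, Wilcoxon power and (gain in points).

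| Assumed shares (%) | Odds ratio 1.5 | Odds ratio 2.0 |
|---|---|---|
| 80/20 | 45.7, 45.3 (−0.4) | 85.0, 84.9 (−0.1) |
| 60/30/10 | 56.0, 66.5 (10.5) | 95.0, 97.6 (2.6) |
| 40/35/20/5 | 58.1, 74.6 (16.5) | 97.4, 99.4 (2.0) |
| 60/30/8/2 | 49.3, 66.3 (17.0) | 92.8, 97.8 (5.0) |
| 80/17/2/1 | 29.7, 45.4 (15.7) | 70.7, 85.0 (14.3) |
| 20/20/20/20/20 | 58.5, 79.1 (20.5) | 97.8, 99.7 (2.0) |
| 70/20/7/2/1 | 37.1, 58.7 (21.6) | 82.3, 94.6 (12.2) |

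The gain is largest where power is in the middle range. It shrinks to 2 to 5 points once Pearson is near its ceiling. Where ratings bunch in the best level, power at an odds ratio of 2.0 is still mid-range and 12 to 14 points remain. In separate runs with 50/35/10/5, 60/30/8/2, 40/40/15/5 and 30/30/20/15/5, both tests held type I error at about 5%.

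**4. Pairs.** The plan matches lesions, so paired tests were simulated on those four distributions at odds ratio 1.5, with independent pairs, and compared with unpaired Pearson. A Cochran-Mantel-Haenszel ridit test stratified by pair gained about 11 to 15 points. In a stratum of two it can record only which lesion is better, so it is a sign test. The Wilcoxon signed-rank test gained about 12 to 14 points with four levels and 19 with five.

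**5. Where the ranking reverses.** With 60/30/8/2 against 60/25/9/6 the groups differ mainly in spread. Pearson power is 62.5%; Wilcoxon power is 8.6%.

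**The case against.** **The scale is not in the documents.** They do not prove that cosmesis will be analysed on more than two levels. The Section 4 quotation is itself a collapsed proportion. If cosmesis is analysed that way, the table is 2 × 2 and no order is left to ignore. This stands, and it makes the point conditional. It does not make collapsing a safe default. For 60/30/8/2 and a shift of 1.5 towards worse ratings, splitting excellent-or-good from the rest gave 36% power, against 72% for the rank test on the full scale. No cut-point is prespecified.

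**The wording leaves room.** Section 12.2 does not say Pearson and ends with a qualifier. A 1-df trend test and the row-mean-score test are themselves Chi-square statistics. A reader might infer that an order-blind test has been prescribed; the text does not go that far. It leaves the choice open and names no ordinal method.

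**Toxicity.** A reader might extend the loss to toxicity. The documents do not say that toxicity is compared by grade. If it is present or absent, nothing is lost.

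**Stakes.** A reader might take cosmesis as a main reason for choosing eBx. Section 4 says radiation was selected for patients in whom surgical resection was not an option, so that goes too far.

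**Direction.** An excess of poor results in one group, without a general shift, is plausible. Step 5 shows that an ordinal test can miss it. This stands as a small downside of the fix.

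**Conclusion.** The point holds conditionally. Chi-square is the only test named, cosmesis is a rating that the background describes in ordered terms, and an ordinary Chi-square test ignores order. With more than two ordered levels and a consistent shift, power is given up.

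The size is a range of about 0 to 25 points: nil with two levels, 3 to 11 with three, about 17 with four and about 22 with five at an odds ratio of 1.5. At 2.0 it is about 2 to 5 points, unless ratings bunch heavily in the best level. A reader might be tempted to quote a single loss of 15 to 23 points. The documents do not support this, because it needs four or five levels, a moderate shift in one direction and mid-range power, none of which they state.

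Steps 2 and 3 treat lesions as independent and unmatched. Severity is low: this concerns secondary endpoints and does not touch the primary comparison.

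**What to change.** In Section 12.2:

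1. State the physician and patient cosmesis scales with their levels, and say whether toxicity is compared by grade or as present/absent.
2. For each cosmesis rating with more than two ordered levels, and for toxicity only if grades are compared, replace Chi-square with an ordinal analysis that allows for matching and for several lesions per patient. One example is a proportional-odds model adjusted for the matching variables of Section 8.2, with patient-clustered standard errors, reporting a common odds ratio and 95% CI.
3. A Wilcoxon signed-rank test on matched pairs can serve as a simpler check. It does not handle several lesions per patient.
4. Do not make the ridit Cochran-Mantel-Haenszel test stratified by pair the main test, since it reduces to a sign test.
5. Report the full category table by group, so that a difference in spread is visible.
6. Keep Chi-square-type tests for binary or unordered items.

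The cost is a few sentences of SAP wording. The methods are available in SAS 9.4, which the plan already names, and no new data or lesions are needed.

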#### THIS SPACE INTENTIONALLY LEFT BLANK

#### **13 GLOSSARY**

TERM OR ABBREVIATION	DEFINITION
BCC	Basal Cell Carcinoma
21 CFR Part 11	Title 21, Code of Federal Regulations Part 11: Electronic Records, Electronic Signatures https://www.accessdata.fda.gov/scripts/cdrh/cfdocs/cfcfr/CFRSearch.cfm? CFRPart=11
CRF	Case Report Form
eBx	Electronic brachytherapy treatment with Xoft
EDC	Electronic Data Capture-internet based secure electronic CRF
NO	No lymph node involvement
M0	No metastases
PRO	Patient Reported Outcomes
SCC	Squamous Cell Carcinoma
Tis	Tumor in stage 0; abnormal cells are found in the squamous cell or basal cell layer of the epidermis; also called carcinoma in situ.
T1	Lesions ≤ 2cm
T2	Lesions $> 2$ and $\le 5$ cm

#### **15 APPENDICES**

#### **15.1 INFORMED CONSENT FORM**

Attached separately in Microsoft® Word® format for edits by IRB and sites.

#### **15.2 CASE REPORT FORM**

Provided as a separate document in the form of a worksheet to use as a source document. The final case report form will be electronic data capture.

#### **15.3 PATIENT REPORTED OUTCOMES (PRO) SURVEY**

Provided as a separate document to be used as a source document with this protocol. The PRO survey results shall be entered into the EDC.
